6.5.10. UP/C and Urine Albumin/Creatinine Ratio (UA/C) Derivation

Missing central laboratory UP/C from subject visits for which the corresponding urine protein or urine creatinine are reported with “<” or “>” will be derived. Urine protein or urine creatinine values reported as “<” or “>” will be imputed as the numeric portion of the result and the ratio will then be derived. If both urine protein and urine creatinine are reported with “<” or “>” then UP/C will not be derived.

The same derivation will be performed for missing central laboratory UA/C using the corresponding urine albumin and urine creatinine results.

6.6. Handling of Missing Data

Tabular summaries of missing data for efficacy endpoints will be prepared per [Section 7.8](#).

6.6.1. Missing Efficacy Endpoints – eGFR and Quantitative Urinalysis

6.6.1.1. Primary Analysis

For the primary analysis of the primary, secondary, and exploratory efficacy endpoints of eGFR and quantitative urinalysis, missing central lab data may be derived per [Section 6.5.9](#) and [Section 6.5.10](#) but will not otherwise be imputed. The primary analysis will analyze all available data based on analysis visit window as described in [Section 6.5.4](#), using the mixed-effects model with random slope and intercepts and the mixed-model repeated measures (MMRM) approaches described in [Section 8.5.1](#), [Section 8.8.1](#), and [Section 8.8.2](#). These models implicitly adjust for missing data through a variance covariance structure.

For the primary analysis of the surrogate endpoint of FPPE, missing data will be imputed according to [Section 6.6.2](#).

6.6.1.2. Sensitivity Analyses

6.6.1.2.1. Multiple Imputations

For the sensitivity analysis of primary and secondary efficacy endpoints of eGFR, missing data will be imputed using the multiple imputation (MI) procedure. Under the missing at random (MAR) assumption, a Bayesian multivariate normal model for the data (including the same covariates as for the primary analysis) will be fitted using a Markov Chain Monte Carlo (MCMC) approach. Quasi-independent samples will be drawn from the posterior distributions for the parameters of the multivariate normal distribution for each arm. A non-informative prior will be used. The MCMC approach allows all missing observations to be imputed, whether a patient has monotone or non-monotone pattern of missingness. Monotone missing pattern is when a data point is missing for an individual patient, all subsequent data points are missing for that patient, whereas a non-monotone missing pattern implies data points are missing in

intermediate visits for a patient. The seed number for the random generator will be defined and documented before study unblinding.

Following the approach described in [Ouyang \(2017\)](#), the following imputation procedures will be implemented:

1. Intermittent missing values before a discontinuation event (ie, discontinuation of randomized therapy or early permanent dropout): The MAR assumption is reasonable for intermittent missing values before a discontinuation event since the values of the endpoint before and after the intermittent missing value are known. Imputation of intermittent missing data will be accomplished using the MCMC option in SAS PROC MI by treatment group to impute intermittent missing data without a monotone missing pattern, prior to performing imputations of values following the discontinuation event.
2. Missing data following a discontinuation event (ie, discontinuation of randomized therapy or early permanent dropout): Impute the post-discontinuation missing data by treatment group under the assumption of MAR using the regression option from the monotone statement of SAS PROC MI. Baseline and post-baseline scheduled visits will be used in the regression option to impute the missing values.
3. Repeat steps 1 and 2 to generate 30 multiply imputed datasets.
4. The mixed-model (ie, the analytic model) analysis described for the endpoint will be performed on each set of the newly “complete” data (observed data plus imputed values).
5. Using Rubin’s approach ([Rubin 1987](#)), the estimated treatment effects are combined across imputations. This will be accomplished using SAS PROC MIANALYZE.

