5.1. Interim Analyses

An unblinded interim analysis will be conducted after 36 weeks following randomization of at least 190 patients (approximately 95 patients per treatment group) to determine whether the surrogate efficacy endpoint, FPPE, is statistically significant. The statistical evaluation of the surrogate efficacy endpoint will be performed using available data from all subjects at the time of interim analysis using a longitudinal mixed model with binary responses, ie, a generalized linear model with logit link function to model the probability of achieving FPPE, at a significance level of $\alpha = 0.05$. Unblinded analysis on select efficacy and safety endpoints will also be conducted.

The interim analysis will be conducted by the unblinded statistical subteam, and only limited analysis results will be disseminated publicly. Full results will not be disseminated among the investigators and those directly involved with ongoing study conduct until after study completion. Details on interim analysis procedures including formation of the unblinded subteam, interim database lock, unblinding procedures, management of unblinded analysis results, and management of documents containing unblinded analysis results will be finalized prior to interim analysis.

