5.4. Changes from Planned Protocol Analyses

The analyses specified in this SAP are consistent with DUPLEX Protocol Amendment 6 with the following exception.

The primary statistical evaluation of the surrogate endpoint, FPPE, will be performed using the Interim Analysis Set (IAS) rather than the subset of patients in the FAS who are scheduled to have completed their Week 36 visit per Section 12.11 of the protocol. Statistical evaluation of FPPE using the subset of patients in the FAS who are scheduled to have completed their Week 36 visit will be performed as a sensitivity analysis.

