6.3.2. Interim Analysis Set

The IAS is the subset of the FAS at the time of the data extraction for interim analysis (per [Section 5.1](#)). Patients in the IAS will be analyzed according to randomized treatment assignment. All analyses conducted at the time of the interim analysis, including primary analysis of the surrogate endpoint and safety analysis, will be based on the IAS.

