6.6.2. Missing Efficacy Endpoints – Responder Endpoints

6.6.2.1. Primary Analysis

For the primary analysis of the surrogate endpoint, missing FPPE will be imputed using the MI procedure outlined in [Section 6.6.1.2.1](#) via imputation of the UP/C result in the natural log scale. Complete UP/C data sets will first be generated via the MI procedure and FPPE outcome for each post-baseline visit subsequently determined. Missing central lab UP/C may be derived per [Section 6.5.10](#) prior to performing imputation via the MI procedure.

For the analysis of all other responder efficacy endpoints, in which patients are classified as either a responder or a nonresponder (binary outcome), any patient who does not have an assessment at the specified time point for the definition of response will be considered a nonresponder (ie, NRI, nonresponder imputation). That is, for the percentage of responders, the patient will be included in the denominator and will not contribute to the numerator.

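### The gating surrogate p-value comes from only 30 imputations, which leaves avoidable Monte Carlo error in a borderline result (minor; a larger number costs only computing time)

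*SAP*

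**What the plan says.** SAP 6.6.2.1 states: "For the primary analysis of the surrogate endpoint, missing FPPE will be imputed using the MI procedure outlined in" Section 6.6.1.2.1. The imputation is done on log UP/C: "Complete UP/C data sets will first be generated via the MI procedure and FPPE outcome for each post-baseline visit subsequently determined". SAP 8.6.1 confirms that missing responses are imputed before the logit model is fitted to responses through Week 60.

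Section 6.6.1.2.1 was written for the eGFR sensitivity analyses. Its step 3 is "Repeat steps 1 and 2 to generate 30 multiply imputed datasets", and it adds: "The seed number for the random generator will be defined and documented before study unblinding". It gives no limit on Monte Carlo error and no rule for raising the number of imputations.

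On who is analysed, SAP 6.3.2 says: "The IAS is the subset of the FAS at the time of the data extraction for interim analysis". SAP 5.1 has the test done "using available data from all subjects at the time of interim analysis". SAP 5.4 discloses that this set is used "rather than the subset of patients in the FAS who are scheduled to have completed their Week 36 visit". The interim takes place 36 weeks after at least 190 patients are randomized, out of about 300 planned (SAP 5.1, 4.3.1).

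Under SAP 8.4 the surrogate is tested at two-sided 0.05, and if it is not significant no further hypothesis is tested in either the US or the non-US hierarchy.

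**The concern.** Multiple imputation draws random values, so the pooled estimate and its p-value vary with the seed. The variation grows with the fraction of missing information (FMI) and shrinks as the number of imputations M rises. Two features of the plan make M worth a second look for this test:

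- The move from the Week 36-eligible subset to the whole Interim Analysis Set can bring in patients with no Week 36 value simply because the visit has not come round. Patients who stopped randomized treatment add to this, because SAP 6.5.4 uses only on-treatment values up to Week 108.
- M = 30 was set for sensitivity analyses of another endpoint and carried over without comment.

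At stake is a single yes/no decision that opens or closes testing of both eGFR slope primaries. Near 0.05, that decision should rest on the data rather than on the random draw.

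**Working it through.** **1. The plan's own figures.** SAP 4.3.1.1 claims at least 90% power with 95 per arm at 50% versus 20%, and a smallest significant difference of about 13%.

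- SE of the difference: pooled √(2×0.35×0.65/95) = 0.0692; unpooled √((0.25+0.16)/95) = 0.0657.
- Power: Φ((0.30 − 1.96×0.0692)/0.0657) = 99.4%, so at least 90% is met.
- Smallest significant difference: 12.6% to 13.6%, depending on the variance used. This agrees with about 13%.
- Expected z under the planned rates: 0.30/0.0692 = 4.33 or 0.30/0.0657 = 4.57.

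**2. Share not yet at Week 36.** The documents do not state it. If all 300 were enrolled when exactly 190 had reached Week 36, it would be (300 − 190)/300 = 37%. This is an upper bound at the planned sample size. Steps 1 and 2 of the procedure name only intermittent gaps and gaps after discontinuation. I read visits not yet due as imputed too, because SAP 6.6.2.1 requires complete data sets.

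**3. Fraction of missing information.** FMI is below the missing share when earlier visits predict Week 36. It has to be assumed:

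- Simulated log UP/C data, with 300 enrolled, 37% not yet due and 10% off drug before Week 36, gave FMI of about 0.27.
- A second simulation with other variances and correlations, 190 at Week 36 out of 300, gave 0.19 to 0.30.
- With 190 out of 250, it gave 0.14 to 0.22.

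I take 0.10 to 0.27 as the working range.

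**4. Seed-to-seed SD of z.** With z = Q/√T and T from Rubin's rules, noise enters through the pooled estimate and through the estimated between-imputation variance:

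SD(z)² ≈ FMI/M + (z/2)² × FMI² × 2/(M − 1)

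At z = 1.96:

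- FMI 0.10, M = 30: 0.00333 + 0.00066, SD 0.063
- FMI 0.27, M = 30: 0.00900 + 0.00483, SD 0.118
- FMI 0.27, M = 200: 0.00135 + 0.00070, SD 0.045

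The first simulation gave SDs of 0.119 (M = 30) and 0.044 (M = 200), which agrees.

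**5. Range of reported p when the exact p is 0.050.** This is 2×(1 − Φ(1.96 ± 1.96×SD)), covering 95% of seeds:

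| FMI | M = 30 | M = 200 | M = 500 | M = 1000 |
|---|---|---|---|---|
| 0.10 | 0.037–0.066 | 0.045–0.056 | 0.047–0.054 | 0.048–0.053 |
| 0.20 | 0.032–0.077 | 0.042–0.059 | 0.045–0.056 | 0.046–0.054 |
| 0.27 | 0.028–0.084 | 0.040–0.061 | 0.044–0.057 | 0.046–0.055 |

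By the same formula, an exact p of 0.04 would be reported as non-significant for about 7%, 17% and 22% of seeds at FMI 0.10, 0.20 and 0.27 with M = 30. With M = 200 the shares are under 0.1%, about 0.7% and about 2%.

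One simulated data set (FMI 0.30, p = 0.046 from 600 imputations) gave p from 0.023 to 0.078 across 20 batches of 30; half the batches fell below 0.05.

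**6. How often it would matter.** The chance that M = 30 gives a different decision from unlimited imputations is about φ(expected z − 1.96) × SD × 0.8. At the planned rates and SD 0.118 this is φ(2.37)×0.118×0.8 = 0.23% or φ(2.61)×0.118×0.8 = 0.12%. The chance of a p between 0.03 and 0.08 is about 0.6%.

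**The case against.** The strongest reply is that nothing here is invalid. Rubin's rules include the finite-M term: at FMI 0.27 it adds about 0.27/30 = 0.9% to the variance, which is under 0.5% of the standard error. The seed is fixed before unblinding, so it cannot be picked to suit. A reader might infer an inflated type I error or an opportunity to choose the seed; the documents support neither. This stands in full. What it leaves is the Monte Carlo error in the one result that will be obtained, which prespecifying the seed does not reduce.

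It is also fair to say that:

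- **The size is illustrative.** The 37% is an upper bound that the plan does not state. The simulations pool a risk difference, stop at Week 36 and leave out the strata and the longitudinal model of SAP 8.6.1. If all 190 patients were due and 12% were missing, the simulated range at M = 30 narrows to 0.039–0.064.
- **Seed-free checks exist.** SAP 8.6.2 plans a CMH test counting missing as non-response in the Week 36-eligible patients, and an observed-case model. They would expose a fragile result, but they cannot reopen the gate.
- **The slopes are a different case.** A reader might infer that the eGFR slope results are noisy for the same reason. They are not. By the final analysis every patient has completed Week 112 or left early (SAP 5.2), so no visit is pending. The slope primaries use no imputation (SAP 6.6.1.1), and imputation there serves sensitivity analyses only (SAP 8.5.2).
- **No M removes the problem exactly at 0.05.** Even 200 leaves 0.040–0.061 at FMI 0.27. This argues for a larger M or an explicit error limit, not for staying at 30.

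**Conclusion.** The point holds as a minor improvement. Thirty imputations are valid but leave avoidable Monte Carlo error in a single gating p-value. At an assumed FMI of 0.27, the 95% seed range around an exact p of 0.050 is about 0.028 to 0.084, against 0.040 to 0.061 with 200. Only results with p of roughly 0.03 to 0.08 are exposed. At the planned 50% versus 20%, the decision would differ from that with unlimited imputations about 0.1% to 0.25% of the time. A reader might infer that the seed is likely to settle the surrogate test; the plan's own assumptions do not support that. The risk becomes material only if the true effect is much smaller than planned.

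The size rests on an assumed FMI of 0.10 to 0.27, on the reading that visits not yet due are imputed, and on a normal approximation rather than the planned model.

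**What to change.** For the surrogate primary analysis and its tipping-point analysis, state in SAP 6.6.1.2.1 step 3 (or in 6.6.2.1) a larger number of imputed data sets: at least 200, preferably 500 to 1000, or as many as are needed to meet a stated Monte Carlo error limit on the p-value. Fix the number or the rule before unblinding, together with the seed, and report the Monte Carlo error of the estimate and the p-value. In the same edit, say how visits not yet due at the data cut are imputed, since steps 1 and 2 do not name them. The larger number may be used for the slope sensitivity analyses too, for consistency only.

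The cost is a short SAP edit and computing time. The data, the estimand and the analysis model do not change.

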6.6.1.2.2. Tipping Point Analysis

To assess the robustness of the results to the MAR assumption, additional sensitivity analyses using the tipping point approach will be used to assess how extreme and detrimental outcomes among patients with missing data must be to overwhelm the treatment effect attained in those patients who had complete data. In these analyses, the same basic analytic model will be used as in the primary analysis, but the MI approach will be expanded to allow for varying impact of missing data by incorporating a shift parameter in the imputation model. The range of values for the shift parameter will explore the varying missing data assumptions, from MAR to missing not at random, including the scenario where imputation model is completely based on the control group (ie, control-based imputation).

For the sparsentan-treated patients, the post-discontinuation imputed values from MI step 3 will be made worse by subtracting a delta defined as k times the treatment differences (means or slopes) obtained for the post-discontinuation visits obtained from the specified mixed model analysis (ie, the analytic model) of the endpoint. No adjustment from the MAR assumption will be implemented for the irbesartan-treated patients (ie, $k = 0\%$).

Generate worse-case scenarios with varying values of k (eg, 100%, 120%, 140%...200%...) until the significance of the prespecified analysis assuming MAR is overturned (eg, from p -value < 0.05 to p -value ≥ 0.05). The worsening by k times the treatment differences is applied to all the post discontinuation imputed values for each set of “complete” data from MI step 3. As an example, if a sparsentan patient had 2 post-discontinuation visits imputed, the values of both of

these 2 imputed visits would be made worse by subtracting k times the sparsentan versus irbesartan treatment differences at these 2 visits.

1. Note that when $k = 0\%$, this approach produces an analysis that is consistent with MAR and is equivalent to the primary analysis with MI.
2. When $k = 100\%$, this approach produces an analysis that is equivalent to “jump to reference,” since the whole treatment differences were subtracted out from the imputations based on the trend of the control group.
3. When $k > 100\%$, the analysis reflects a “worse-than-control” specification.

6.6.1.3. Local Labs

The primary analyses will use central lab data only. As a sensitivity analysis, local lab data will be included with central lab data.

6.6.2. Missing Efficacy Endpoints – Responder Endpoints

6.6.2.1. Primary Analysis

For the primary analysis of the surrogate endpoint, missing FPPE will be imputed using the MI procedure outlined in [Section 6.6.1.2.1](#) via imputation of the UP/C result in the natural log scale. Complete UP/C data sets will first be generated via the MI procedure and FPPE outcome for each post-baseline visit subsequently determined. Missing central lab UP/C may be derived per [Section 6.5.10](#) prior to performing imputation via the MI procedure.

For the analysis of all other responder efficacy endpoints, in which patients are classified as either a responder or a nonresponder (binary outcome), any patient who does not have an assessment at the specified time point for the definition of response will be considered a nonresponder (ie, NRI, nonresponder imputation). That is, for the percentage of responders, the patient will be included in the denominator and will not contribute to the numerator.

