8.8.4. Other Responder Endpoints

The following responder endpoints will be summarized descriptively for FAS at both the interim and final analysis and compared (at final analysis only) between treatment groups using a CMH test controlling for the randomization variables:

- The proportion of patients reaching a confirmed 40% reduction in eGFR, ESRD, or death. ESRD is defined as initiation of RRT or sustained eGFR <15 mL/min/1.73² during the study (confirmed after repeat assessment of at least 14 days after initial assessment)
- The proportion of patients reaching a confirmed 30% reduction in eGFR, ESRD, or death
- The proportion of patients requiring initiation or intensification in immunosuppressive medication during the study
- The proportion of patients undergoing reduction in immunosuppressive medication during the study

Reduction of eGFR requires confirmation by a value at least 4 weeks after the initial value. If the last value on randomized treatment is the initial value for reduction or eGFR <15 mL/min/1.73² then the last value on randomized treatment is considered confirmed or sustained.

Initiation of RRT will be entered on the Concomitant Procedures eCRF as “chronic dialysis” or “kidney transplant” and on the Adverse Events eCRF as “progression of CKD leading to chronic dialysis” or “progression of CKD requiring kidney transplant”.

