8.8.8. Other Time-to-Event Endpoints

For the time-to-event analyses, patients who do not experience an event will be censored at the time of analysis (if still on randomized treatment) or the time of randomized treatment discontinuation (whichever is earlier). Treatment groups will be compared using a log rank test stratified by the randomization stratification variables for FAS at both interim and final analysis. KM estimates of the distribution of the time-to-event will be tabulated and graphed by treatment group. The tabulation will include the KM estimate of the medians and corresponding 95% CIs, if the medians can be estimated.

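### Counting missing patients as nonresponders is applied, by class label, to the kidney-loss/ESRD/death composites, where it means event-free

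*SAP*

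**What the plan says.** SAP 6.6.2.1 gives FPRE its own treatment (multiple imputation). For all remaining binary responder efficacy endpoints, "any patient who does not have an assessment at the specified time point for the definition of response will be considered a nonresponder", and it spells out the arithmetic: "the patient will be included in the denominator and will not contribute to the numerator".

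SAP 8.8.4, under the title Other Responder Endpoints, opens: "The following responder endpoints will be summarized descriptively for FAS at both the interim and final analysis". Its list starts with "The proportion of patients reaching a confirmed 40% reduction in eGFR, ESRD, or death" and "The proportion of patients reaching a confirmed 30% reduction in eGFR, ESRD, or death", followed by initiation or intensification of immunosuppression and then its reduction. The arms are compared at the final analysis with a CMH test controlling for the randomisation variables. Protocol 12.7.3 specifies the same test for the 40% composite.

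SAP 8.8.4 also has ascertainment rules of its own. "Reduction of eGFR requires confirmation by a value at least 4 weeks after the initial value", but a qualifying value that is the last one on randomised treatment counts without confirmation. Initiation of renal replacement therapy (RRT) is taken from the procedure and adverse event forms.

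SAP 6.6.2.2 adds an observed-cases analysis for all responder endpoints. SAP 8.8.8 describes time-to-event methods ("Treatment groups will be compared using a log rank test stratified by the randomization stratification variables") but does not name the composites, and it censors at discontinuation of randomised treatment. Protocol 12.10.3 covers missing data only for continuous endpoints and UP/C response.

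**The concern.** Missing-as-nonresponse is cautious when response is a benefit: an unseen patient cannot add to apparent efficacy. When the so-called response is kidney loss or death, the same rule becomes the favourable assumption, because an unseen patient is scored as having done well. Nothing in either document reverses the rule for unfavourable outcomes.

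The on-treatment convention adds to the problem. Under SAP 6.5.4 and 8.1, efficacy visits through Week 108 use only values up to 3 days after the last dose. Protocol 6.4.2 nevertheless encourages patients who stop drug to keep attending through Week 112. Read together, an eGFR loss first seen after stopping drug can go uncounted even when it was measured. The CMH test takes no account of how long each patient was observed.

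At stake is the between-arm comparison on kidney failure and death, which readers will weigh despite its exploratory label.

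**Working it through.** The documents state no event rate, dropout rate or power for these composites, so there is no planned figure to reproduce. Every rate below is an assumption. The sample size, about 150 per arm, is from SAP 4.3.1.

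**1. Bias with no true difference.** Assume a constant hazard λ over two years (time scaled to 1), two-year risk r = 1 − e^(−λ), and discontinuers lost at a uniformly distributed time with the same hazard as everyone else. The share of discontinuers whose event is seen before loss is s = 1 − (1 − e^(−λ))/λ. Each discontinuer therefore lowers the observed rate by r − s. The false difference between arms is (r − s) × the gap in discontinuation.

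| r | λ | s | r − s | gap 10 points | gap 15 points |
|---|---|---|---|---|---|
| 15% | 0.1625 | 7.70% | 7.30% | 0.73 | 1.09 |
| 25% | 0.2877 | 13.10% | 11.90% | 1.19 | 1.79 |

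The arm with more loss shows 0.7 to 1.8 points fewer events. The standard error of the difference at 150 per arm is 3.9 to 4.8 points here, so the bias is about 0.2 to 0.4 standard errors.

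**2. If discontinuers have twice the hazard.** Their true risk is 27.75% (r = 15%) or 43.75% (r = 25%); the part seen is 14.63% or 23.96%.
- Smallest case: true excess 0.10 × (27.75 − 15) = 1.3 points; observed 0.10 × (14.63 − 15) = −0.04.
- Largest case: true excess 0.15 × (43.75 − 25) = 2.8 points; observed 0.15 × (23.96 − 25) = −0.16.

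A real excess of 1.3 to 2.8 points shows as about zero.

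**3. A second model, and the observed-cases analysis.** Let d be dropout and f the share of dropouts' events seen before they leave. The rate under the rule is (1 − d)r + d·r·f. Take r = 20% in both arms, f = 0.25 and dropout 30% versus 15%:
- Arm with 30% dropout: 0.70 × 0.20 + 0.30 × 0.20 × 0.25 = 15.5%.
- Arm with 15% dropout: 0.85 × 0.20 + 0.15 × 0.20 × 0.25 = 17.75%.
- False difference 2.25 points; standard error √(0.155 × 0.845/150 + 0.1775 × 0.8225/150) = 4.30 points.
- Chance of a significant result favouring the arm with more loss: Φ(−1.96 + 2.25/4.30) = 7.5%, against a nominal 2.5%.
- Observed cases, keeping dropouts with an event and removing those without: 0.155/0.715 = 21.7% versus 0.1775/0.8575 = 20.7%. The error now runs the other way.

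**4. Equal dropout.** With r = 20%, d = 20% and f = 0.25 in both arms, both read 0.80 × 0.20 + 0.20 × 0.20 × 0.25 = 17%, with no bias in the difference. With a true 18% versus 30%, d = 20% and f = 0.5, the rates read 16.2% versus 27.0% and power falls from 68% to 62%.

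**The case against.** Coverage is by class label. The rule in 6.6.2.1 turns on a specified time point, and the composites have none: they ask whether an event was reached during the study, under ascertainment rules of their own. Any simple proportion over the FAS would count patients without a recorded event as non-events. This stands as a reason to clarify the wording. It does not remove the effect, since an event-free dropout is scored as a non-event either way.

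A reader might infer that everyone who drops out is counted as having kept their kidneys. The documents do not support that. Events recorded before loss count, a qualifying last on-treatment eGFR counts without confirmation, and RRT comes from case report forms. Protocol 10.5 requires chronic dialysis and transplant to be reported as serious adverse events, and Protocol 6.6 includes mortality searches in tracing. The models in steps 1 and 2 treat discontinuation as complete loss of ascertainment and omit the last-value rule, so they overstate the problem for RRT and death in particular.

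A reader might also infer that these are the trial's only clinical outcomes, so that an excess of harm would be hidden. Hospitalisations are analysed in SAP 8.8.6, and adverse events are summarised on study under SAP 10. Nor do the documents show that the rule favours sparsentan: the direction depends on which arm loses more patients, which is unknown.

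Finally, a time-to-event analysis is no complete cure. In the doubled-hazard cases, Kaplan-Meier estimates censored at loss recover about 0.75 to 1.8 points of a true 1.3 to 2.8, roughly 60%. Counting off-drug eGFR events changes the on-treatment convention, and replacing CMH would depart from the protocol. These points stand and shape the fix.

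**Conclusion.** The concern holds for patients lost without a recorded qualifying event. As written, the SAP scores them as event-free on the kidney-loss, ESRD or death composites, and no provision reverses this for harms. The last-value rule, form-based capture of RRT and the observed-cases analysis soften the effect but do not recover unseen events. The same polarity applies to initiation or intensification of immunosuppression.

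The size rests entirely on assumed rates: 0.7 to 1.8 points toward the arm with more loss when risk is 15-25% and the discontinuation gap is 10-15 points. Bias in the difference requires unequal loss, or a different risk among those lost. With equal and otherwise similar loss, both rates are understated and some power is lost.

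A reader might infer that the trial's main result is in doubt. It is not: SAP 3.2.3 lists the composites as exploratory, outside the hierarchy in SAP 8.4. The point should still be corrected because the correction is cheap.

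**What to change.** - In SAP 6.6.2.1, state that nonresponder imputation does not apply to unfavourable-event endpoints: both eGFR/ESRD/death composites, and initiation or intensification of immunosuppression.
- Keep the CMH proportions, which the protocol specifies for the 40% composite.
- Add a time-to-first-confirmed-event analysis of the composites: log-rank test and Cox model, both stratified by the randomisation factors, censored at last eGFR or vital-status contact. SAP 8.8.8 cannot be reused unchanged, because it censors at treatment discontinuation.
- Add two sensitivity analyses: one counting events through Week 112 on or off drug, and one counting missing as an event or using multiple imputation. The second is needed because censoring alone does not remove bias from informative dropout.
- Record the change in SAP 5.4.

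The cost is SAP wording and a few extra exploratory analyses. The protocol's CMH test and the on-treatment convention of the main efficacy analyses stay in place.
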